Cover Page

The impact of Therapeutic Exercises on the Quality of Life and Shoulder Range of Motion in
Women after a Mastectomy, a RCT.

June 30, 2018

Submitted November 27, 2019

Protocol: The Institution Review Board (IRB) of the university and the medical center granted approval for the study. Seventy-six women were approached while waiting for their surgery after approval from their surgeon. Women who showed interest in participating signed a consent form and were then randomly assigned to one of two groups by flipping a coin. Thirty women ended up in the intervention group and 30 in the control group. Figure one details the protocol of the study. The intervention group received pre-surgery education and training on therapeutic exercises in addition to the routine hospital care. The control group, which had 30 patients, received the routine hospital care that did not include any exercise training or education. Routine hospital care included explanation by the surgeon on the surgical procedure with follow up at two and four weeks after discharge. The educational material was developed by the principal investigator (PI) and included a power point and a booklet with instructions on the exercises as well as information about the surgery and what to expect after the surgery. The educational material was based on previous research and adopted to our population after consultation with a panel of experts including two nurses and three physicians. Eligible women were approached while waiting for their appointment with their surgeon. If they showed interest in participating they signed a consent form. The PI explained the study and what is involved in participating including the weekly phone calls for women in the intervention group. Participants were told that they will be visited at home by the PI to assess their ROM and to fill out a questionnaire.

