The intervention: The intervention consisted of three phases. Phase 1 took place the day prior to surgery at which time the intervention and control, groups completed the QoL-BC survey and shoulder ROM was measured using the goniometer. Phase 2 consisted of one to one education with the intervention group prior to surgery. Education consisted of a power point presentation regarding the therapeutic exercises, information about the surgery and a booklet with pictures of the exercises to take home. In this phase demonstration of the exercises by the researcher with a return demonstration by the patient was done to ensure proper techniques. The researcher called the patients at home every week to ensure that the women were continuing the exercises. Phase 3 was conducted for both groups in the patient's homes and entailed reassessment of shoulder ROM and completing the QoL-BC at the second and fourth week after discharge. All patients completed the study. The exercises included deep breathing as well as shoulder exercises such as extension of the triceps, biceps curl, paddling in sitting position, fluttering with both arms, hands behind neck, forward wall crawls, and side wall crawls.

Patients were instructed to perform 10 repetitions of each exercise during hospitalization, with further guidance at the outpatient follow-up appointment. Shoulder flexion was limited to 90° of active assisted

ROM for the first few days post-surgery and until the drains were removed, then gradually increased after the third postoperative day. Patients were instructed to keep performing the exercises after discharge.

Results

Patient characteristics

There were no differences between groups at baseline. The majority of the patients in both groups were between 35 and 42 years of age, roughly 70% were married, and the majority of patients had a high school or higher education.

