Shoulder range of motion scores: While the shoulder ROM scores were not significantly different between groups prior to surgery, there were significant differences at the second and fourth weeks after surgery (Table 2). Flexion at two weeks for the intervention group was 133.80 ± 6.79 and for the control group it was 131.17 ± 2.20 , $p = 0.001$, at four weeks it was 167.97 ± 4.09 for the intervention group and 159.92 ± 1.73 for the control group, $p < 0.001$. Extension significantly improved for the study group at two weeks with a mean of 42.77 ± 2.30 versus 38.73 ± 1.46 , $p < 0.001$ and at four weeks 53.07 ± 2.12 versus 49.03 ± 1.25 , $p < 0.001$. Additionally, abduction demonstrated a significant difference between the study and control groups at two weeks 143.50 ± 4.42 versus 138.57 ± 1.78 , $p < 0.001$ and at four weeks 167.03 ± 4.61 versus 159.40 ± 1.69 , $p < 0.001$.

Differences between groups on each of the QoL-BC 4 subscales: There were no significant differences between groups at baseline on the QoL survey with both groups having low QoL scores. However, there were significant differences between groups at two and four weeks after surgery on the four subscales (Table 3). Physical well-being was significantly improved with the study group experiencing higher level of physical well-being than the control group; at two weeks, 58.37 ± 6.16 versus 50.23 ± 7.78 , $p = 0.001$, and at four weeks 66.67 ± 6.19 versus 54.97 ± 9.55 , $p < 0.001$. For Psychological well-being there was significant difference between the two groups at two weeks, the study group mean 142.33 ± 15.48 and the control group 122.93 ± 7.34 , $p < 0.001$, and at four weeks, 169.50 ± 26.43 and 145.67 ± 12.44 , $p < 0.001$. Social well-being at two weeks was significantly higher for the study group 43.57 ± 7.045 versus 29.30 ± 8.30 for the control group, $p < 0.001$; and at four weeks 54.33 ± 8.73 for the study group versus 42.33 ± 5.08 for the control group, $p < 0.001$. Spiritual well-being was significantly improved at two weeks, with a mean for the study group of 51.07 ± 4.37 versus 44.90 ± 6.05 , $p < 0.001$; and at four weeks 56.33 ± 3.96 versus 48.93 ± 2.61 , $p < 0.001$.

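### The two-week flexion p = 0.001 does not follow from its own means and SDs, and all 14 comparisons are called significant with no stated primary outcome, test, alpha or multiplicity rule

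*Combined protocol and SAP*

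**What the plan says.** Under Results, the paragraph on shoulder range of motion (ROM) states that "there were significant differences at the second and fourth weeks after surgery (Table 2"), and reports flexion, extension and abduction at each visit. The paragraph on the QoL-BC subscales states that "there were significant differences between groups at two and four weeks after surgery on the four subscales", and reports the physical, psychological, social and spiritual subscales at each visit. Twelve of these results carry p < 0.001. The other two carry p = 0.001:

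- Two-week flexion: "Flexion at two weeks for the intervention group was 133.80 ± 6.79" and "for the control group it was 131.17 ± 2.20 , $p = 0.001".
- Two-week physical well-being: "at two weeks, 58.37 ± 6.16 versus 50.23 ± 7.78 , $p = 0.001".

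On numbers, the Protocol section says "Thirty women ended up in the intervention group and 30 in the control group". The section on the intervention says "All patients completed the study", and describes "reassessment of shoulder ROM and completing the QoL-BC at the second and fourth week after discharge".

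The text names no primary outcome or primary visit, no significance level, no statistical test and no rule for handling several comparisons. Tables 2 and 3 are not in the copy reviewed; that is not held against the document.

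**The concern.** There are two linked problems.

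First, the printed p-value for two-week flexion looks too small. The groups differ by 2.63 degrees and the intervention SD is 6.79, so a p-value of 0.001 with 30 per arm is surprising.

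Second, significance is claimed on every measure at both visits, but nothing says which comparison answers the trial's question or how error is controlled across the set. A claim that covers every comparison is only as sound as its weakest member, and two-week flexion is that member. At stake is whether the ROM statement may include flexion at two weeks, and whether a reader can tell what error rate stands behind the full list.

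**Working it through.** **Inputs.** Means and ± values come from the two Results paragraphs. There are 30 women per arm (Protocol), and all completed (intervention section), so n = 30 per arm at both visits. The ± values are taken as SDs. Read as standard errors, they would give t = 8.05/√(4.09² + 1.73²) = 1.81 for four-week flexion, which cannot be p < 0.001. Alpha is not stated; two-sided 0.05 is assumed.

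**Step 1: number of comparisons.** 3 motions × 2 visits + 4 subscales × 2 visits = 6 + 8 = 14.

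**Step 2: the printed flexion p-value.**

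- Difference = 133.80 − 131.17 = 2.63.
- SE = √(6.79²/30 + 2.20²/30) = √(50.94/30) = 1.303.
- t = 2.63/1.303 = 2.02.
- Pooled test, 58 df: p = 0.048, 95% CI 0.02 to 5.24.
- Welch test, df = (50.94/30)² / {[(46.10/30)² + (4.84/30)²]/29} = 35.0: p = 0.051, 95% CI −0.02 to 5.28.
- Normal approximation: p = 0.044. One-sided pooled test: p = 0.024.
- Other splits of the 60 women, with 24 to 38 in the intervention arm: p = 0.03 to 0.08.

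None of these comes near 0.001. With these means and SDs, the pooled p would round to 0.001 only from 78 per arm.

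**Step 3: all 14 comparisons.**

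| Comparison | Difference | Printed p | Pooled p | Welch p |
|---|---|---|---|---|
| Flexion, wk 2 | 2.63 | 0.001 | 0.048 | 0.051 |
| Flexion, wk 4 | 8.05 | <0.001 | 4.0e-14 | 3.1e-12 |
| Extension, wk 2 | 4.04 | <0.001 | 3.8e-11 | 1.2e-10 |
| Extension, wk 4 | 4.04 | <0.001 | 1.4e-12 | 8.8e-12 |
| Abduction, wk 2 | 4.93 | <0.001 | 4.8e-7 | 1.6e-6 |
| Abduction, wk 4 | 7.63 | <0.001 | 8.6e-12 | 3.3e-10 |
| Physical, wk 2 | 8.14 | 0.001 | 3.4e-5 | 3.6e-5 |
| Physical, wk 4 | 11.70 | <0.001 | 5.5e-7 | 8.3e-7 |
| Psychological, wk 2 | 19.40 | <0.001 | 6.3e-8 | 2.2e-7 |
| Psychological, wk 4 | 23.83 | <0.001 | 3.7e-5 | 6.0e-5 |
| Social, wk 2 | 14.27 | <0.001 | 1.5e-9 | 1.7e-9 |
| Social, wk 4 | 12.00 | <0.001 | 2.0e-8 | 4.7e-8 |
| Spiritual, wk 2 | 6.17 | <0.001 | 3.0e-5 | 3.4e-5 |
| Spiritual, wk 4 | 7.40 | <0.001 | 7.5e-12 | 2.3e-11 |

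The 12 results printed as p < 0.001 all reproduce. Two-week physical well-being recomputes to a smaller value than printed, so its conclusion does not change.

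**Step 4: multiplicity.**

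- Bonferroni threshold: 0.05/14 = 0.0036.
- Printed p-values: all are 0.001 or less, so adjusted values are at most 14 × 0.001 = 0.014 and all 14 pass.
- Recomputed p-values, Bonferroni: flexion at two weeks becomes 0.68 (pooled) or 0.72 (Welch). The largest of the others becomes 14 × 0.0000603 = 0.00084.
- Recomputed p-values, Holm: flexion at two weeks has the largest p and is tested last, at the full 0.05. Its adjusted p equals its own p, 0.048 or 0.051.

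**Step 5: familywise error of the procedure.** If all 14 nulls are true and the tests are independent, 1 − 0.95¹⁴ = 51%. With a common correlation of 0.3, 0.5, 0.7 or 0.9, simulation gives about 44%, 35%, 25% or 14%. At a per-test level of 0.01 the independent figure is 13%; at 0.001 it is 1.4%.

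**The case against.** The strongest reply is that multiplicity changes nothing here. Every printed p-value passes Bonferroni, and on recomputed values Holm tests flexion at the same 0.05 it would face unadjusted. This stands. Under Holm, flexion turns on the choice between two t-tests with nearly the same p-value, and its weakness comes from a printed p-value that its own figures do not support.

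A second reply is that the test is unnamed. An analysis of change from baseline, a baseline-adjusted analysis or a rank test could give another p-value, and the two-week table is not available. This also stands. It is why the mismatch calls for reconciliation, and why no verdict of 13 out of 14 can be fixed in advance.

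A third reply is that choosing Welch now is itself a choice made with results in view, and it is the one that tips flexion over 0.05. That is fair as a caution. The case for Welch does not rest on flexion alone: the intervention SD exceeds the control SD in all six ROM comparisons, by a factor of 1.6 (2.30/1.46) to 3.1 (6.79/2.20). It should be applied to all 14 and declared as a later choice.

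A reader might infer that there is a 51% chance that the reported findings include a false one. The documents do not support that. The figure assumes that every null is true, which 13 p-values at or below about 0.00006 make untenable, and it rests on an alpha that the text does not state.

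**Conclusion.** The point holds in a limited form. The two-week flexion result is not secure: its printed p = 0.001 is inconsistent with its printed means and SDs, which give 0.048 or 0.051. This assumes that ± denotes SD, that 30 per arm were analysed, and that the test compared the two-week values directly. The other 13 comparisons, including four-week flexion and all eight QoL-BC results, are unaffected by any standard correction.

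The missing primary outcome, test, alpha and multiplicity rule is a real gap. It leaves the general claim without a stated error rate, but on these figures it overturns no printed result. The 51% is only a ceiling for the procedure under the conditions in Step 5. Nor do the figures show that flexion at two weeks is unaffected by the intervention: the Welch interval runs from −0.02 to 5.28 degrees.

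**What to change.** 1. Recompute the two-week flexion comparison from patient data, reconcile the p-value with the means and SDs, and correct whichever is wrong. Check the two-week physical well-being p-value at the same time.
2. State the test, its sidedness and the alpha used.
3. If the IRB-approved protocol named a primary outcome and visit, use it and label the rest secondary. If it did not, do not choose one now that results are known. Treat the 14 comparisons as one family, re-run them with an unequal-variance test and Holm adjustment, report adjusted p-values, and say that the method was chosen after the results.
4. Unless the re-analysis supports two-week flexion, reword the ROM statement to exclude it.

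The cost is a few lines of text and one re-run on existing data. The downside is the possible loss of one claimed result.

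### The p = 0.001 printed for two-week physical well-being does not match a two-sample t-test on its own figures (p about 0.00003); a minor reporting error if a t-test was used

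*Combined protocol and SAP*

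**What the plan says.** The Results paragraph on the four QoL-BC subscales gives a mean, a ± value and a p-value for each subscale at two and four weeks. Physical well-being at two weeks (intervention first) reads "58.37 ± 6.16 versus 50.23 ± 7.78 , $p = 0.001".

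Two other entries in that paragraph serve as comparators:
- psychological well-being at four weeks: "169.50 ± 26.43 and 145.67 ± 12.44 , $p < 0.001"
- spiritual well-being at two weeks: "51.07 ± 4.37 versus 44.90 ± 6.05 , $p < 0.001"

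On group size, the Protocol section says "Thirty women ended up in the intervention group and 30 in the control group", and the section on the intervention says "All patients completed the study". I therefore take 30 per arm at two weeks.

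The Results report 14 between-group comparisons after surgery: six for range of motion and eight for quality of life. Twelve are printed as p < 0.001. The two printed as p = 0.001 are this one and shoulder flexion at two weeks, "133.80 ± 6.79 and for the control group it was 131.17 ± 2.20 , $p = 0.001". The document names no test, sidedness, covariate adjustment or multiplicity rule for any of them, and it does not say whether the ± values are SDs.

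**The concern.** A mean, an SD and a sample size in each of two independent groups fix the t-test p-value. Here the printed p is well above the one that the printed figures imply, while neighbouring results of the same strength carry p < 0.001. One t-test procedure applied to the printed figures would not give these entries different labels.

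Quality of life is in the trial's title, and anyone reusing this result for an effect size or a meta-analysis needs the mean, SD and p-value to agree. As printed, the reader cannot tell whether the p-value is a typographical slip, the output of an unnamed method, or something else. Only the investigators can settle that.

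**Working it through.** **Inputs.** Physical well-being at two weeks: 58.37 ± 6.16 (intervention) and 50.23 ± 7.78 (control), from the QoL-BC paragraph; n = 30 per arm, from the Protocol section and the statement on completion. Assumptions: the ± values are SDs, the groups are independent, and the test is a two-sided t-test.

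**Attempt to reproduce p = 0.001.**
- Difference = 58.37 − 50.23 = 8.14
- SE = √((6.16² + 7.78²)/30) = √((37.95 + 60.53)/30) = √3.282 = 1.81
- t = 8.14/1.812 = 4.49
- p = 0.000034 (pooled, 58 df) or 0.000036 (Welch, 55 df)
- 95% CI = 8.14 ± 2.00 × 1.812 = 4.5 to 11.8

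The printed figure is not reproduced: 0.001/0.000034 is about 29.

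**Same calculation on the comparators.**

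| Comparison | Difference | SE | t | p pooled | p Welch | Printed |
|---|---|---|---|---|---|---|
| Physical, 2 weeks | 8.14 | 1.81 | 4.49 | 0.000034 | 0.000036 | = 0.001 |
| Psychological, 4 weeks | 23.83 | 5.33 | 4.47 | 0.000037 | 0.000060 | < 0.001 |
| Spiritual, 2 weeks | 6.17 | 1.36 | 4.53 | 0.000030 | 0.000034 | < 0.001 |
| Flexion, 2 weeks | 2.63 | 1.30 | 2.02 | 0.048 | 0.051 | = 0.001 |

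**Could a variant give 0.001 for physical well-being?**
- Worst-case rounding of the printed means and SDs (Welch): 0.000038.
- One-sided: 0.000017.
- Bonferroni, pooled test: × 8 = 0.00027 and × 14 = 0.00048, both below 0.0005.
- Bonferroni × 14, Welch test: 14 × 0.0000364 = 0.00051, which does round to 0.001. But four-week psychological well-being would then be 14 × 0.0000603 = 0.00084, which also rounds to 0.001 and is printed as < 0.001. Two-week flexion would be 14 × 0.0513 = 0.72. This route does not reconcile the printed set.
- Fewer women analysed: about 19 per arm would give 0.001, against 30 stated.
- Mann-Whitney test, simulated on samples of 30 forced to the printed means and SDs (1,500 draws for each of 16 pairs of distribution shapes): median p between about 0.000006 and 0.00009. Values rounding to 0.001 came up in 0.1% of draws with both arms normal and in at most 4.9%, with the arms strongly skewed in opposite directions.

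**The case against.** The strongest objection is that the mismatch is conditional. With no test named, the p-value could come from a rank test, a covariate-adjusted or repeated-measures model, or a multiplicity-adjusted analysis. Under a rank test, two outcomes with nearly equal t need not have nearly equal p, because the shape of each distribution matters. This stands as a limit on the wording. The rank-test route is unlikely in simulation but not excluded, and the document describes no model or adjustment that would produce the figure.

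A reader might go further and infer that p = 0.001 could not have come from these data, so that either the p-value or the summary figures must be wrong. The document does not support that. One can solve backwards: at the printed difference, t = 3.47 (p = 0.001) needs an SE of 8.14/3.47 = 2.35, hence a common SD of about 9.1 instead of 7.0; at the printed SDs, it needs a difference of about 6.3 instead of 8.1. These are hypotheticals that assume both a t-test and a correct p-value. Nothing in the text suggests that the means or SDs are wrong. With 12 of 14 results printed as p < 0.001, a substituted symbol is the simplest explanation, though that too is an inference. Table 3, which is cited for these results, is not in the text available, so it could not be checked for a test name or an exact p.

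It is also fair to say that the consequence is small. The printed p is larger than the recomputed one, no primary outcome is designated, and this is one subscale at one of two time points.

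**Conclusion.** The point holds as a minor reporting discrepancy. On the printed figures an unadjusted two-sample t-test gives p about 0.00003 where the document prints 0.001, and results of almost identical strength in the same paragraph carry a different label. The discrepancy understates the evidence, and the difference is significant at 5% on either figure. The conclusion rests on three assumptions: the ± values are SDs, 30 women per arm were analysed at two weeks, and a t-test was used. It does not extend to any error in the means or SDs.

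The other p = 0.001 in the Results deserves attention in the same check. Two-week flexion recomputes to 0.048 (pooled) or 0.051 (Welch). That mismatch runs in the direction that favours the intervention, and whether the result reaches 5% depends on which version of the test is used.

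**What to change.** 1. Recompute two-week physical well-being from the source data. If it was a t-test and the means and SDs are right, report the difference of 8.1 (95% CI 4.5 to 11.8) with p < 0.001.
2. If another test or model was used, name it and apply it to all 14 comparisons.
3. State that the ± values are SDs, if they are.
4. Include two-week flexion in the same recheck.

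The cost is one check of two comparisons against source data, a sentence naming the test, and corrected figures where needed. If a different test has to be applied throughout, the 14 comparisons need one rerun.
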